11.0 Statistical Considerations

Power calculation.

In a prior cluster-randomized cluster-crossover trial in the same ICU,⁵¹ 880 mechanically ventilated adults were enrolled per year (73.3 per month), with a median of 22 VFDs [IQR 0-25 VFDs] and an intra-cluster intra-period correlation of 0.01. During the planned 36-month PILOT trial, we estimate 2,640 mechanically ventilated adults will be admitted to the study ICU, of whom 390 will be enrolled during washout periods and excluded from the primary analysis and 2,250 will be included in the primary analysis. With a total enrollment of 2,250 patients, a standard deviation in the primary outcome of VFDs of 11.4 days, and a two-sided alpha of 0.05, ***the PILOT trial will have 92 percent statistical power to detect an absolute difference between groups in VFDs of 2.0 days*** (similar to the numerical difference in VFDs between SpO₂ target groups reported in prior studies^{29,30}).

Primary analysis of the Primary Outcome.

The primary analysis will be an intention-to-treat comparison of the primary outcome of VFDs between the higher, intermediate, and lower SpO₂ target groups among all patients enrolled in the trial except [1] those admitted during one of the 7-day washout periods and [2] those with a laboratory-confirmed diagnosis of Coronavirus disease 2019 (COVID-19). We will use a proportional odds model with independent covariates of group assignment (higher, intermediate, or lower SpO₂ target) and time. Time (in days) will be treated as a continuous variable with values ranging from 1 (first day of enrollment) to 1,097 (final day of enrollment) and will be analyzed using restricted cubic splines with multiple knots to allow for non-linearity resulting from seasonality or secular trends. For the purposes of declaring a statistically significant

difference between groups in the primary endpoint, we will consider the conditional effect from the proportional odds model and a two-sided P value of 0.05. In addition to the overall comparison of the three study groups, we will perform pair-wise comparisons between the lower and intermediate groups, lower and higher groups, and intermediate and higher groups using the same statistical approach.

Sensitivity Analyses of the Primary Outcome

- We will repeat the primary analysis using alternative statistical approaches to comparing the VFDs outcome between groups. These statistical approaches will include:
 - zero-inflated Poisson regression;

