For each of the 18 two-month blocks during the 36 months of enrollment in the PILOT trial, the medical ICU is assigned to a single SpO₂ target (cluster-level

allocation). Every two months, the ICU will switch between use of a lower SpO₂ target (target 90% and goal range 88-92%), use of an intermediate SpO₂ target (target 94% and goal range 92-96%), and use of a higher SpO₂ target (target 98% and goal range 96-100%) in a randomly generated sequence (cluster-level crossover) (Figure 2). The order of study group assignments for each two-month block was generated by computerized randomization using permuted blocks of 3 to minimize the impact of seasonal variation and temporal changes. For the 36 months of enrollment in the PILOT trial, patients receiving invasive mechanical ventilation in the ED for whom admission to the medical ICU is planned will receive the same SpO₂ target assigned to the medical ICU. The study did not enroll in April and May of 2020 due to disruptions in research and clinical care from the Coronavirus Infectious Disease 2019 (COVID-19) pandemic (Figure 2).

Washout Periods

The last 7 days of each two-month block are considered an analytic washout period during which the ICU continues to target the assigned SpO₂ but data from new patients are not included in the primary analysis. Assuming a median duration of mechanical ventilation of 3 [IQR 3-5] days, a 7-day washout period will ensure that 98% patients in the primary analysis do not experience a “crossover” from a period assigned to one assigned SpO₂ target to a period assigned to another SpO₂ target. Data from patients admitted during washout periods will be included in a pre-specified sensitivity analysis (see *Statistical Analysis* section). Any patient who does remain mechanically ventilated in the study ICU through a crossover from a period assigned to one SpO₂

target to a period assigned to another SpO₂ target will be analyzed in the SpO₂ target group to which the ICU was assigned at the time of the patient's enrollment in the trial (intention-to-treat analysis).

Study Interventions

Choice of SpO₂ targets

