In a prior cluster-randomized cluster-crossover trial in the same ICU [51], 880 mechanically ventilated adults were enrolled per year (73.3 per month), with a median of 22 VFDs [IQR 0-25 VFDs] and an intra-cluster intra-period correlation of 0.01. We estimate 2,640 mechanically ventilated adults will be admitted to the study ICU during the 36-month PILOT trial, of whom 390 will be excluded from the primary analysis for initial receipt of invasive mechanical ventilation in a study location during a washout period and 2,250 will be enrolled and included in the primary analysis. With a total enrollment of 2,250 patients, a standard deviation in the primary outcome of VFDs of 11.4 days, and a two-sided alpha of 0.05, we calculated using a t-test that the PILOT trial will have 92 percent statistical power to detect an absolute reduction in VFDs of 2.0 days (similar to the numerical difference in VFDs between SpO₂ target groups reported in prior studies [22,24]).

Data and Safety Monitoring Board and Interim Analysis

An independent Data and Safety Monitoring Board (DSMB) oversees the trial. On March 23, 2020 the DSMB conducted a single, planned interim analysis at the anticipated halfway point of the trial and recommended the trial continue without modification (see DSMB charter in online supplemental file 2 and details of interim analysis in supplemental file 1, section 22). The DSMB is composed of two physicians outside the study institution with expertise in adult pulmonary and critical care medicine clinical practice and clinical research, one bioethicist, and one biostatistician.

Statistical Analysis Principles

R (R Foundation for Statistical Computing, Vienna, Austria) will be used for analyses. Analyses will be conducted at the level of an individual patient during an individual hospitalization in an intent-to-treat fashion, unless otherwise specified. Continuous variables will be reported as mean \pm SD or median and IQR; categorical variables will be reported as frequencies and proportions.

Main Analysis of the Primary Outcome

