The main analysis will be an intention-to-treat comparison of the primary outcome of VFDs between the higher, intermediate, and lower SpO₂ target groups among all patients enrolled in the trial except [1] those admitted during one of the 7-day washout periods and [2] those with a laboratory-confirmed diagnosis of COVID-19. Patients with a diagnosis of COVID-19 will be excluded from the main analysis for two reasons. First, the majority of the PILOT trial occurred prior the COVID-19 pandemic, with too few two-month study blocks occurring during the pandemic to ensure balance in the number of patients with COVID-19 between trial groups. Second, at the study hospital, ICU patients diagnosed with COVID-19 are transferred to a separate, dedicated COVID-19 ICU that was not participating in the PILOT trial. Thus, patients with COVID-19 are unlikely to have received significant exposure to the SpO₂ target intervention in the PILOT trial. Patients enrolled during washout periods and patients diagnosed with COVID-19 will be included in sensitivity analyses (see *Sensitivity Analyses* below).

It is possible to estimate a conditional effect, which is interpreted as the effect of a given SpO₂ target on an individual patient given the values of the covariates for that

patient, or a marginal effect, which is interpreted as the population effect of implementing a given SpO₂ target as a general policy [52]. Since an SpO₂ target intervention may be applied both at the patient level as an individual intervention and at the unit level as a general policy, both may be of interest.

To estimate the conditional effect, we will use a proportional odds model with independent covariates of group assignment (higher, intermediate, or lower SpO₂ target) and time [53,54]. Time (in days) will be treated as a continuous variable with values ranging from 1 (first day of enrollment) to 1,097 (final day of enrollment) and will be analyzed using restricted cubic splines with multiple knots to allow for non-linearity resulting from seasonality or secular trends. For the purposes of declaring a statistically significant difference between groups in the primary endpoint, we will consider the conditional effect from the proportional odds model and a two-sided P value of 0.05.

To estimate the marginal effect, we will use generalized estimating equations (GEE) with study period as the cluster and an independent variable for group assignment (higher, intermediate, or lower SpO₂ target).

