2. Free-day outcomes—defined as whole calendar days from last receipt of therapy until 28 days (online supplemental file 1, section 19)
 - i. Vasopressor-free days
 - ii. Renal replacement therapy-free days
 - iii. ICU-free days

iv. Hospital-free days

Exploratory organ function outcomes

1. Daily non-respiratory Sequential Organ Failure Assessment (SOFA) score (online supplemental table S1)⁴⁷
2. Plasma creatinine concentration (mg/dL)
3. Plasma lactate concentration (mmol/L)
4. Presence of acute respiratory distress syndrome by Berlin criteria⁴⁸
5. Stage II or greater acute kidney injury (AKI) by Kidney Disease: Improving Global Outcomes creatinine criteria.⁴⁹

Exploratory safety outcomes

1. Atrial arrhythmia
2. Ventricular arrhythmia
3. Cardiac arrest with return of spontaneous circulation
4. Pneumothorax or pneumomediastinum
5. Ischaemic stroke
6. Myocardial infarction⁵⁰

Additional long-term patientimportant outcomes

The independently funded Cognitive Outcomes in the Pragmatic Investigation of Optimal Oxygen Targets (CO-PILOT) study (R21AG063126) will assess cognitive, physical and psychological outcomes at 12 months after enrolment in the PILOT trial. The protocol and statistical analysis plan for the CO-PILOT study will be published separately.

Statistical analysis and reporting

Sample size estimation and power calculation

In a prior cluster-randomised cluster-crossover trial in the same ICU,⁵¹ 880 mechanically ventilated adults were enrolled per year (73.3 per month), with a median of 22 VFDs (IQR: 0–25 VFDs) and an intracluster intra-period correlation of 0.01. We estimate 2640 mechanically ventilated adults will be admitted to the study ICU during the 36-month PILOT trial, of whom 390 will be excluded from the primary analysis for initial receipt of invasive mechanical ventilation in a study location during a washout period and 2250 will be enrolled and included in the primary analysis. With a total enrolment of 2250 patients, a SD in the primary outcome of VFDs of 11.4 days, and a two-sided alpha of 0.05, we calculated using a t-test that the PILOT trial will have 92% statistical power to detect an absolute reduction in VFDs of 2.0 days (similar to the numerical difference in VFDs between SpO₂ target groups reported in prior studies^{22 24}).

DSMB and interim analysis

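### The 92% power is for a pairwise t-test on independent patients; the intra-period correlation of 0.01 quoted beside it is not used, and at face value it gives about 54-62%

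*Combined protocol and SAP*

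**What the plan says.** The SAP (Sample Size Estimation and Power Calculation) takes from a previous cluster-crossover trial in the same ICU 880 ventilated adults a year and "an intra-cluster intra-period correlation of 0.01". It expects 2,640 admissions over 36 months, "of whom 390 will be excluded from the primary analysis" because they fall in washout periods, which leaves 2,250. With an SD of 11.4 days and "a two-sided alpha of 0.05", it says "we calculated using a t-test that the PILOT trial will have 92 percent statistical power" for a 2.0-day reduction.

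The published SAP repeats this: "the PILOT trial will have 92% statistical power to detect an absolute reduction in VFDs of 2.0 days". So does section 11.0 of the protocol dated 4/7/2021, without naming the test: "the PILOT trial will have 92 percent statistical power to detect an absolute difference between groups in VFDs of 2.0 days".

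Two other SAP sections bear on the figure:

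- **Randomization and Treatment Allocation.** One target is assigned to the whole ICU for a period: "For each of the 18 two-month blocks during the 36 months of enrollment in the PILOT trial".
- **Main Analysis of the Primary Outcome.** "For the purposes of declaring a statistically significant difference between groups in the primary endpoint, we will consider the conditional effect", from a proportional odds model with group and a time spline. It has no term for period. Period enters only as the cluster in a GEE for the marginal effect, which does not decide significance.

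None of these places gives a design effect, an inter-period correlation, or the number of patients per comparison.

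**The concern.** Patients treated in the same two-month period share staffing, season and case mix, and they all receive the same target. If outcomes are correlated within a period, 750 patients in 6 periods carry less information about a target than 750 independent patients. The plan quotes a correlation for exactly this, then reports a power that takes no account of it. The sponsor's other material does treat period as a source of variation: the GEE clusters on it, and the DSMB charter's interim model has a random period effect.

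Two things are at stake. A reader of a null result would be told that a true 2.0-day difference had only an 8% chance of being missed. And the protocol's interim-analysis text and the DSMB charter tie a request to extend enrolment to projected power below 80%. Without clustering, 80% power needs 2 × (1.960 + 0.842)² × 11.4² / 2.0² = about 510 per group, or 1,530 in total, so that trigger would be far away. With the 0.01 at face value, power is already below 80% at the planned 2,250.

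**Working it through.** **Inputs.** From the SAP power section: 2,250 analysed patients, SD 11.4, difference 2.0, two-sided alpha 0.05, intra-period correlation (WPC) 0.01. From the SAP allocation section: 18 periods. Derived: 2,250/3 = 750 patients per target, 18/3 = 6 periods per target, 2,250/18 = 125 patients per period. Not in the documents: the inter-period correlation (BPC), varied here from 0 to 0.01.

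**1. The plan's figure.** SE = 11.4 × √(2/750) = 0.589. The noncentral t power with 1,498 df is 92.4%, which reproduces the plan. Other readings do not fit:

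- 1,125 vs 1,125: 98.6%
- Bonferroni-corrected pairwise test: 84.1%
- three-group F-test: 94.9% for means 2/0/0, 86.9% for means 0/1/2

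So the figure is pairwise and unadjusted.

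**2. With clustering.** Design effect DE = 1 + 124 × WPC − 125 × BPC. The BPC term is the part of the correlation shared by all periods, which cancels in the crossover. For WPC 0.01 and BPC 0:

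- DE = 1 + 1.24 = 2.24
- effective N = 2,250/2.24 = about 1,004
- SE = 0.589 × √2.24 = 0.881

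Power is shown for a normal reference and for t with 15 df (pooled over three arms) and 10 df:

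| BPC (assumed) | DE | Normal | t, 15 df | t, 10 df |
|---|---|---|---|---|
| 0 | 2.24 | 62.2% | 56.5% | 53.6% |
| 0.002 | 1.99 | 67.3% | 61.5% | 58.5% |
| 0.005 | 1.615 | 76.2% | 70.5% | 67.4% |
| 0.008 | 1.24 | 86.2% | 81.4% | 78.5% |
| 0.01 | 0.99 | 92.7% | 89.0% | 86.7% |

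The 10-df column charges for randomisation blocks but credits no variance removed by them, so it is a low end. A simulation of period means (200,000 replicates) at BPC 0 gave 62.4%, 56.7% and 53.9%.

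**3. Detectable difference and break-even points.** At DE 2.24, 80% power needs a difference of 2.47 (normal), 2.64 (15 df) or 2.74 (10 df) VFDs. For 2.0 VFDs, 80% power needs DE no larger than 1.471, 1.284 or 1.193. Since BPC = (2.24 − DE)/125, this means BPC of at least 0.0062, 0.0076 or 0.0084. For 92% (normal), DE must be at most 1.019, so BPC is about 0.0098.

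**4. A smaller WPC.** With BPC 0, WPC 0.005 gives 67-76% and WPC 0.001 gives 82-89%.

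**5. Three-group test.** F with 2 and 15 df at DE 2.24: about 55% for means 2/0/0 and 43% for means 0/1/2.

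**6. Planned model.** A linear analogue (group plus time spline with 3 or 5 knots, no period term, the protocol's sequence, independent period effects with SD √0.01 × 11.4 = 1.14) rejects lower versus higher at 2.0 days in 84% and 78% of runs. It also rejects in 19% and 18% when there is no effect, so the first pair is not power at 5%.

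**Side note.** Washout covers 18 × 7 = 126 days. At 880 a year that is 880 × 126/365 = about 304 patients, not 390. The mismatch is conservative: 2,640 − 304 = 2,336 patients would raise the unadjusted power only to 93.3%.

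**The case against.** The strongest reply is that 54-62% comes from one corner of the range. A BPC of 0 is the least favourable non-negative value, and the documents do not support it over any other. Nor do they say whether the 0.01 was estimated for VFDs, over what period length, or from how many units. These points stand: the low figure is conditional and must be shown with its range.

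The second reply is that the time spline is meant to absorb season and secular trend, and the period-level powers give it no credit. This stands in part. If period variation is a smooth drift or an annual wave rather than independent from period to period, the same linear analogue keeps null rejection at roughly 4-9% and has power of mostly 80-91%. Only slow drift (correlation length about a year, an assumption) fitted with 3 knots came out at about 92-93%. So smooth drift can bring power close to the stated figure, but the plan neither makes nor defends that assumption, and its t-test contains no time adjustment. Under independent period effects the spline does not rescue the analysis.

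The third reply is that pairwise 95% confidence intervals are planned and enrolment has ended. Both are true, and they limit the damage. They do not make the published power statement correct.

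**Conclusion.** The concern holds. That the 92% leaves out the quoted correlation is certain and needs no assumption: the figure is the power of one pairwise comparison of independent patients. The size of the loss is conditional. With the 0.01 at face value and nothing shared between periods, a pairwise test that holds 5% error has about 54-62% power for 2.0 VFDs and would miss such a difference in about 38-46% of trials rather than 8%. Power rises as more of the 0.01 is shared by all periods or removed as smooth drift, and the plan gives no ground for assuming that nearly all of it is. The clustered figures take equal periods of 125 and describe a period-level test on means, not the rejection rate of the planned proportional odds model. The missing period term in that model is a separate matter of type I error. The statement should be corrected; enrolment, outcomes and analysis are not affected by this point.

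**What to change.** Change the power paragraphs in the SAP and in protocol section 11.0, for example to:

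> The 92% figure is for a pairwise t-test without clustering. With 18 periods of about 125 patients, an intra-period correlation of 0.01 and an assumed inter-period correlation of 0 (design effect 2.24), pairwise power for 2.0 VFDs is about 54-62%, and the difference detectable with 80% power is about 2.5 VFDs (normal approximation; 2.6-2.7 with 15 or 10 df). For inter-period correlations of 0.002, 0.005 and 0.008, power is 58-67%, 67-76% and 78-86%.

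Also:

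- Give the power of the three-group test for both patterns, 2/0/0 and 0/1/2.
- State which outcome, period length and number of units the 0.01 came from and, if the previous trial's data allow, give the inter-period correlation.
- If the spline is expected to recover power, say so and state the drift assumption.
- Reconcile the 390 washout exclusions with 126 washout days.

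The cost is a few sentences. No patients, outcomes or analyses change; the stated power becomes less favourable.

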4.0 Study Description

In order to address the aims outlined above, we propose the Pragmatic Investigation of optimal Oxygen Targets (PILOT) trial. The PILOT trial will be a prospective, un-blinded, cluster-randomized, cluster-crossover trial conducted between July 1, 2018 and August 31, 2021 in the medical ICU at Vanderbilt University Medical Center examining the effect of SpO₂ targets on days alive and free of mechanical ventilation among mechanically ventilated ICU patients. For the 36 months of enrollment in the PILOT trial, the entire medical ICU will be assigned to a single SpO₂ target and the ICU will switch between lower, intermediate, and higher SpO₂ targets every two months in a

randomly generated sequence (Figure below). Patients who fulfill inclusion criteria without meeting exclusion criteria will be enrolled at the initiation of mechanical ventilation in the study ICU or in the emergency department when admission to the study ICU is planned. The PILOT trial will control only the SpO₂ target and all other aspects of patients' clinical care will remain at the discretion of the treating clinicians.

Study Year 1						Study Year 2						Study Year 3					
Jul-Aug	Sep-Oct	Nov-Dec	Jan-Feb	Mar-Apr	May-Jun	Jul-Aug	Sep-Oct	Nov-Dec	Jan-Feb	Mar & Jun	Jul-Aug	Sept-Oct	Nov-Dec	Jan-Feb	Mar-Apr	May-Jun	Jul-Aug
2018						2019						2020					
High	Mid.	Low	Mid	Low	High	Low	Mid.	High	High	Mid.	Low	Mid.	High	Low	Mid.	High	Low

The study ICU was randomly assigned to an SpO₂ target for each two-month block. The study did not enroll in April and May of 2020 secondary to the COVID-19 pandemic.
High = SpO₂ target 98% (range 96-100%), Mid = SpO₂ target 94% (range 92-96%), Low = SpO₂ target 90% (range 88-92%)

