For both approaches, in addition to assessing for an overall group effect within the model, we will estimate the differences between each pair of SpO₂ targets by extracting 95% confidence intervals from the model.

Sensitivity Analyses of the Primary Outcome

- We will repeat the primary analysis using alternative statistical approaches to comparing the VFDs outcome between groups such as zero-inflated Poisson

regression or zero-inflated negative binomial regression, global rank scale analysis [55], and Fine and Gray competing risk regression.

- We will repeat the primary analysis with adjustment for pre-specified baseline covariates of age, sex, race and ethnicity, source of ICU admission, vasopressor receipt, and acute diagnoses at enrollment, and severity of illness as assessed by the non-respiratory SOFA score.
- We will repeat the primary analysis replacing the continuous covariate of time with a categorical covariate of season defined as: winter (January, February, March); spring (April, May, June); summer (July, August, September); and fall (October, November, December).
- We will repeat the primary analysis among all patients enrolled in the trial, including [1] patients initiated on invasive mechanical ventilation in a study location during one of the pre-specified 7-day washout periods and [2] patients with a diagnosis of COVID-19.

Analysis of Effect Modification for the Primary Outcome

We will examine whether pre-specified baseline variables modify the effect of study group on the primary outcome using formal tests of statistical interaction in a proportional odds model. Independent variables will include study group assignment, the potential effect modifier of interest, and the interaction between the two (e.g., study group * presence of sepsis or septic shock) and time. Significance will be determined by the P value for the interaction term, with values less than 0.10 considered to suggest a potential interaction and values less than 0.05 considered to confirm an interaction.

We will examine whether the following baseline variables modify the effect of study group on the primary outcome:

1. Age;
2. Race and ethnicity (Hispanic, Non-Hispanic Black, Non-Hispanic White, Other);
3. Source of admission to the ICU (ED, hospital ward, another ICU in the study hospital, operating room, outside hospital);
4. Duration of invasive mechanical ventilation prior to enrollment;
5. Chronic comorbidities (categories are not mutually exclusive)

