It is possible to estimate a conditional effect, which is interpreted as the effect of a given SpO₂ target on an individual patient given the values of the covariates for that patient, or a marginal effect, which is interpreted as the population effect of implementing a given SpO₂ target as a general policy.⁵² Since an SpO₂ target intervention may be applied both at the patient level as an individual intervention and at the unit level as a general policy, both may be of interest.

To estimate the conditional effect, we will use a proportional odds model with independent covariates of group assignment (higher, intermediate or lower SpO₂ target) and time.^{53 54} Time (in days) will be treated as a continuous variable with values ranging from 1 (first day of enrolment) to 1097 (final day of enrolment) and will be analysed using restricted cubic splines with multiple knots to allow for non-linearity resulting from seasonality or secular trends. For the purposes of declaring a statistically significant difference between groups in the primary endpoint, we will consider the conditional effect from the proportional odds model and a two-sided p value of 0.05.

To estimate the marginal effect, we will use generalised estimating equations with study period as the cluster and

an independent variable for group assignment (higher, intermediate or lower SpO₂ target).

For both approaches, in addition to assessing for an overall group effect within the model, we will estimate the differences between each pair of SpO₂ targets by extracting 95% CIs from the model.

Sensitivity analyses of the primary outcome

- ▶ We will repeat the primary analysis using alternative statistical approaches to comparing the VFDs outcome between groups such as zero-inflated Poisson regression or zero-inflated negative binomial regression, global rank scale analysis⁵⁵ and Fine and Gray competing risk regression.
- ▶ We will repeat the primary analysis with adjustment for prespecified baseline covariates of age, sex, race and ethnicity, source of ICU admission, vasopressor receipt, acute diagnoses at enrolment, and severity of illness as assessed by the non-respiratory SOFA score.
- ▶ We will repeat the primary analysis replacing the continuous covariate of time with a categorical covariate of season defined as: winter (January, February, March); spring (April, May, June); summer (July, August, September); and fall (October, November, December).

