To account for non-linear relationships, continuous variables will be analyzed using restricted cubic splines with between 3 and 5 knots.

24. Corrections for Multiple Testing

We have pre-specified a single primary outcome and a single secondary outcome. Consistent with recommendations of the Food and Drug Administration [65] and the European Medicines Association [66], each will be tested using a two-sided p-value with a significance level of 0.05. For all other analyses, emphasis will be placed on the estimate of effect size with 95% confidence intervals, as recommended by the *International Committee of Medical Journal Editors* [67], and no corrections for multiple comparisons will be performed.

25. Handling of Missing Data

The primary outcome of VFDs is not anticipated to be missing for any patients.

Missing data will not be imputed for the primary outcome or any secondary or exploratory outcomes. None of the covariates pre-specified for the adjusted analysis are anticipated to be missing for any patients. In additional adjusted analyses, any missing data for covariates will be imputed using multiple imputations.

26. Rationale for Waiver of Informed Consent

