April 5, 2021	Original Statistical Analysis Plan submitted for publication
August 25, 2021	Statistical Analysis Plan submission completed peer review
August 31, 2021	Final patient enrolled
October 28, 2021	Final Statistical Analysis Plan* published: [name], [name], [name], [name], [name], [name], [name], [name], [name], [name], [name], [name], [name], [name], [name], [name]; PILOT Investigators and the Pragmatic Critical Care Research Group. Protocol and statistical analysis plan for the Pragmatic Investigation of optimal Oxygen Targets (PILOT) clinical trial. BMJ Open . 2021 Oct 28;11(10):e052013. PMID: 34711597

**No changes to content of the statistical analysis plan occurred between submission of the Protocol and Statistical Analysis Plan and its publication.*

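### Does leaving the knot number of the time spline unstated let enough seasonality into the group comparison to require a change to the plan?

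*Combined protocol and SAP*

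**What the plan says.** The main analysis is a proportional odds model with group and time as covariates, and it alone decides statistical significance (SAP, Main Analysis of the Primary Outcome; the 7 April 2021 protocol, section 11.0, agrees). Time is a day count from 1 to 1,097 that "will be analyzed using restricted cubic splines with multiple knots to allow for non-linearity resulting from seasonality or secular trends". The published SAP says the same: "analysed using restricted cubic splines with multiple knots to allow for non-linearity resulting from seasonality or secular trends". The revision sequence at the end of the SAP dates completion to 2 April 2021, last enrolment to 31 August 2021 and publication to 28 October 2021, and notes that "No changes to content of the statistical analysis plan occurred between submission of the Protocol and Statistical Analysis Plan and its publication".

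The only knot number is in section 23 of the supplement, on baseline covariates for the adjusted sensitivity analysis: "continuous variables will be analyzed using restricted cubic splines with between 3 and 5 knots". The mortality model lists group and time and does not repeat the spline (SAP, Analysis of the Secondary Outcome).

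Season and trend also appear elsewhere. Targets were allocated "using permuted blocks of 3 to minimize the impact of seasonal variation and temporal changes". A sensitivity analysis is planned as follows: "We will repeat the primary analysis replacing the continuous covariate of time with a categorical covariate of season". There is a covariate-adjusted analysis, and a before/during-pandemic interaction. The protocol's allocation table (section 4.0) notes that "The study did not enroll in April and May of 2020 secondary to the COVID-19 pandemic".

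**The concern.** One smooth term has to carry a secular trend, a pandemic and about three yearly cycles. A restricted cubic spline with few knots over three years cannot bend often enough to follow a yearly cycle. Permuted blocks of three balance the targets within each half-year but do not force balance by time of year, and the realised calendar is uneven: every analysed September-October day is on the intermediate target, and July-August and November-December have no intermediate days.

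If VFDs vary with season, part of that variation could be read as a target effect in the test that decides the trial, and by how much depends on a number the plan does not give. The season sensitivity analysis replaces time instead of joining it, so no planned model is stated to hold both.

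**Working it through.** **The plan's own figure.** With 750 per group, SD 11.4, a difference of 2.0 and two-sided 0.05 (SAP, Sample Size Estimation), the pairwise SE is 11.4 × √(2/750) = 0.589. Power is Φ(2.0/0.589 − 1.96) = Φ(1.44) = 92.5%, which matches the stated 92%.

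**Calendar.** From the protocol's allocation table, 1 July 2018 to 31 August 2021 is 1,158 days. Removing the 61 days of April-May 2020 gives 1,097, the SAP's last index value. Removing 18 × 7 = 126 washout days leaves 971 analysed days:

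| Months | Higher | Intermediate | Lower |
|---|---|---|---|
| Jul-Aug | 55 | 0 | 165 |
| Sep-Oct | 0 | 162 | 0 |
| Nov-Dec | 108 | 0 | 54 |
| Jan-Feb | 53 | 52 | 52 |
| Mar-Apr | 0 | 85 | 54 |
| May-Jun | 108 | 23 | 0 |
| Total | 324 | 322 | 325 |

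**Leakage.** Assume uniform enrolment and a sinusoidal yearly cycle of amplitude A (half of peak to trough). Regress the sine and cosine of calendar date on group plus the spline, with knots at standard quantiles. For each contrast the worst-phase leakage is √(b_sin² + b_cos²). For the largest contrast, as a fraction of A:

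| Knots | Worst phase | Range over phases | Average |
|---|---|---|---|
| no time term | 0.25 | 0.12-0.25 | 0.19 |
| 3 | 0.20 | 0.12-0.20 | 0.16 |
| 4 | 0.19 | 0.10-0.19 | 0.15 |
| 5 | 0.40 | 0.09-0.40 | 0.26 |
| 6 | 0.54 | 0.09-0.54 | 0.35 |
| 10 | 0.08 | 0.00-0.08 | 0.05 |

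The planned season factor, used alone, leaves 0.28 in intermediate versus lower.

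**Size in VFDs.** The documents give no seasonal amplitude, so A is an assumption. An upper limit comes from treating the whole intra-period correlation of 0.01 as one sinusoid: A²/2 = 0.01 × 11.4², so A = 1.61 days. Type I error is for the 2-df group test (noncentral chi-square, 2,250 patients), given this calendar and with season as the only period effect, for 3 to 5 knots:

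| A (days) | Worst-phase bias (days) | Type I error, worst phase | Type I error, phase average |
|---|---|---|---|
| 0.5 | 0.1-0.2 | 5.2-5.8% | 5.1-5.4% |
| 1.0 | 0.2-0.4 | 5.8-8.1% | 5.5-6.7% |
| 1.61 | 0.3-0.6 | 7.0-13.6% | 6.3-9.5% |

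**Luck of the draw.** Over 3,000 re-drawn permuted-block sequences on the same calendar, median worst-phase leakage is 0.62, 0.64 and 0.67 with 3, 4 and 5 knots. The realised 0.20, 0.19 and 0.40 lie near the 1st, 1st and 10th percentiles.

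**Would an annual sine and cosine pair do better?** Against a pure sinusoid it leaves zero, but only because the model then contains the curve being tested. It has two limits.

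- *Variance.* Averaged over phases, the squared bias removed is A² × leakage²/2. The price is the added variance. For intermediate versus lower with 3 knots, leakage is 0.200 and variance inflation rises from 1.014 to 1.028, which adds about 0.0050 (0.589² times the unrounded increase). The two are equal when A = √(2 × 0.0050)/0.200 = 0.50 days. Over all contrasts and 3 to 5 knots the break-even lies between 0.47 and 0.55 days.
- *Shape.* Take a smooth but peaked yearly cycle (von Mises, concentration 2, amplitude 1; an assumed shape). Average leakage over peak dates goes from 0.32 to 0.30 with 3 knots, 0.33 to 0.32 with 4, and 0.39 to 0.35 with 5. For a mid-January peak it rises: 0.15 to 0.22, 0.16 to 0.23, and 0.23 to 0.25.

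Ten knots without the pair reduce leakage but inflate the contrast variance by 20 to 45%, which lowers pairwise power to 81-87%.

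**The case for a change.** The best case for a change is that the choice is open and it matters. The phrase in the SAP covers anything from 0.08 to 0.54 of the amplitude, and leakage does not fall steadily with more knots: five or six do worse than no time term. The plan itself names seasonality as a job for the spline, and enrolment closed without a number. Two extra parameters cost little with 3 or 4 knots (variance inflation 1.01 to 1.08). If the cycle is sinusoidal with an amplitude of 1 day, they pay. With 5 knots, the phase-averaged mean squared error of higher versus lower falls from 1.143 × 0.347 + 0.397²/2 = 0.475 to 1.206 × 0.347 = 0.418.

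The missing number stands, as does the sensitivity of the contrasts to it under a large sinusoidal cycle. Three things weaken the case. The 3-to-5 range is borrowed from a section about other covariates. The statement that a fixed share of any yearly cycle remains is too strong, since the figures depend on when the cycle peaks and on its being a sinusoid. And the SAP text was complete five months before the last enrolment, so late publication does not show that the wording was left open with outcomes in view.

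The primary model also states no period effect, so leftover seasonal variation is not reflected in its standard errors. That is a question about period-level variation in general, which no knot number settles.

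**Conclusion.** The plan omits a detail, and no change follows from it. The number and placement of knots, and the form of time in the mortality model, are settings that the analyst must fix in code and can fix sensibly from the calendar alone.

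The possible harm is bounded and rests on assumptions: with 3 to 5 knots and a sinusoidal cycle of 0.5 to 1 day, the bias is at most 0.1 to 0.4 days against a planned difference of 2.0, and phase-average type I error is 5.1 to 6.7%. The 13.6% figure needs 5 knots, the least favourable peak date and the whole intra-period correlation in one sinusoid. All of this is conditional on one calendar, which is better balanced on a yearly cycle than most that the randomisation could have produced.

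No remedy clearly dominates. A sine and cosine pair breaks even at about half a day of amplitude and does little for a peaked cycle. Ten knots cost 5 to 11 points of power. A season factor leaves 0.27 to 0.28 of a sinusoid, with or without the spline. None separates a September-October effect from the intermediate target, because all those days were assigned to it. Competent statisticians would choose differently among these, and a fairly flexible time spline with season as a sensitivity analysis is a fair choice. A documented seasonal effect on VFDs of a day or more in this ICU would alter this judgement; the documents contain none.
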